1. PROTOCOL SYNOPSIS

Study title: A cohort study on the association between acid-suppressing drugs and seizures using THIN database in the UK.

AZ study identifier(s): D9612N00017 Acid-suppressing Drug Seizure Epidemiology Study

Principal Investigator:

Co-Investigator:

Type of study, study design: Retrospective cohort study with nested case control analysis.

Study objective(s): To estimate the incidence of seizure in the general population and stratified by epilepsy status.

To estimate the relative risk of seizure associated with use of PPI and H2RA and stratified by epilepsy status.

Setting: The Health Improvement Network (THIN) primary care database in the UK.

Study population: All individuals aged 20–84 years from 1 January 2005 to 31 December 2011 who have been enrolled with their PCP (Primary Care Physician) for at least 2 years and have a computerized prescription history of at least 1 year. Patients will have to be free of acid-suppressing drugs (PPI or H₂RAs) for at least one year, and never have a diagnosis of cancer, alcohol abuse or alcohol-related disease, or drug abuse. When an individual meet all these eligibility criteria that date will be marked as start date. Patients aged ≥ 70 years with a follow-up longer than 1 year will be excluded from the study population if they have fewer than two recorded consultations with a PCP during their entire follow-up (proxy for incomplete and invalid data recording). All remaining individuals will constitute the final study cohort.

All members of the study cohort will be followed until the earliest of: first record of seizure, a diagnosis of cancer, alcohol abuse or alcohol-related disease, or drug abuse, age of 85 years, death or end of study period (31 December 2011).

To ascertain the number of cases with a diagnosis of seizure, epidemiologists at will manually review the electronic medical records of patients, including free-text comments, with suppressed personal identifiers and information on drug use removed to

allow for a blinded revision of patient profiles. A random sample of potential cases will be further validated for accuracy of diagnosis through questionnaires to the PCP.

A nested case-control analysis will be conducted comparing incident cases with a new episode of seizure versus controls selected with incidence density sampling. The final size of the control sample will be determined by being at least four times the size of the final list of cases and be a round number.

Exposure definition: All prescriptions issued by the PCP are recorded in the database and a coded drug dictionary (Multilex) is used to record prescribed medicines. Details of every prescription issued include date, dosage, quantity dispensed, duration of therapy, and indication.

Medication will be categorized in the nested case-control analysis as follows: *current use* when the supply of the most recent prescription lasted until the index date; *recent use*, when the supply of the most recent prescription ended 1–90 days before the index date; *past use*, when the supply of the most recent prescription ended 91–365 days before the index date; and non-use, when there was no recorded use of the relevant medication in the 365 days before the index date.

In THIN, acid-suppressing drugs include PPIs: lansoprazole, omeprazole, rabeprazole, pantoprazole, esomeprazole and H2RAs: cimetidine, famotidine, nizatidine, ranitidine

Outcome definition: A patient with an incident diagnostic code for a seizure during follow-up will be accepted as a case if the patient was referred to a consultant, and/or admitted to hospital for the event.

Statistical analysis: A nested case–control analysis will be performed to assess the effect of potential risk factors for seizure using unconditional logistic regression. In this analysis all patients ascertained with an incident episode of seizures will be used as cases. The control group will comprise a random sample of subjects frequency-matched by calendar year (described in section 4.6). Under our study design of incidence density sampling, the odds ratio (OR) is an unbiased estimator of the incidence rate ratio (RR) (Rothman 2002).

To determine the association between study outcome and current use of PPI and H₂RA, we will run unconditional logistic regression models and compute the OR and their 95% confidence intervals (95%CI). The estimates will be adjusted for the frequency-matched variable (calendar year), age, sex, time to event and other independent risk factors. Sub-analyses will be repeated in the strata of individuals with epilepsy and individuals free of epilepsy.

Study strengths: A major strength of this study is that use of THIN enables analysis of an extensive sample of PPI users that is representative of the UK primary-care population, with a similar age and sex distribution to those in the national population supporting a broad external validity of our findings and generalizability. Also, the risk in another drug class (H₂RA) that shares similar treatment indication than PPI will be analyzed to verify the specificity of the results. Validation of the outcome with the PCP

will help to reduce the extent of outcome misclassification when working with automated databases.

Study limitations: A potential limitation of the study is that use of acid suppressing drugs could be misclassified in some instances. For example, the recording of a PPI prescription in THIN does not necessarily mean that the patient actually took the medication, although it is likely that patients with repeating prescriptions do take their medication as there is a prescription almost every month. Also, lack of recording of OTC acid suppressing drugs is another source of misclassification. This misclassification of drug exposure will most likely be non-differential and thus will bias the effect estimates towards the null. Therefore, it should be noted that to the extent that misclassification due to lack of OTC acid suppressing drug recording occurs in our study population, our effect estimates will tend to underestimate the true risk.

Outcome missclassification of seizure will be substantially reduced with the two step validation process: first obtaining free text comments for the review of the patient profiles and second direct validation with the PCP. The extent of recording of comorbidity, medication use and life style habits in THIN will help to minimize as much as possible potential confounding by any of these variables.

2. INTRODUCTION

A seizure is an abnormal, unregulated electrical discharge that occurs within the brain's cortical grey matter and transiently interrupts normal brain function. Due to the numerous properties that control neuronal excitability there are many different causes of seizures and epilepsy. In principal these relate to differences between individuals in the susceptibility or threshold of seizures (e.g. genetic factors), concomitant conditions with a high likelihood of leading to seizures (e.g. traumatic brain injury) and precipitating factors, intrinsic (e.g. psychological stress, sleep deprivation) and exogenous (e.g. certain medications) (Lowenstein 1998).

Seizures may be acute symptomatic or unprovoked. Acute symptomatic seizures are seizures occurring at the time of a systemic insult or in close temporal association with a documented brain insult. (Hauser and Beghi 2008). Unprovoked seizures are seizures occurring in the absence of precipitating factors and may be caused by a static injury (remote symptomatic seizures) or a progressing injury (progressive symptomatic seizures) (Hauser and Beghi 2008). The International League Against Epilepsy (ILAE) has defined epilepsy as “a disorder characterized by an enduring predisposition to generate epileptic seizures and by neurobiologic, cognitive, psychological and social consequences of this condition. This definition requires the occurrence of at least one epileptic seizure” (Fisher et al. 2005). The Commission on Epidemiology and Prognosis (1993) has recommended the use of the term acute symptomatic seizures as separate from the unprovoked seizures that define epilepsy in epidemiology studies (Beghi et al 2010).

The incidence of acute symptomatic seizures has been estimated to be 29–39 per 100,000 per year across several studies, regions and time periods. These predominate in men, in the youngest age class, and in the elderly (Hauser and Beghi 2008). Traumatic brain injury, cerebrovascular disease, drug withdrawal, and metabolic insults are the most common causes. In recent studies, the incidence of unprovoked seizures has been estimated to be 46-57 per 100,000 person-years. As with epilepsy, single unprovoked seizures predominate in men and in patients less than 12 months and older than 65 years (Hauser and Beghi 2008). Seizure etiology is the single most important risk factor for the increased mortality in patients with a first seizure (Hauser and Beghi 2008).

Drugs associated with the development of convulsion/seizure include cocaine, other CNS stimulants, cyclosporine, tacrolimus, pentylenetetrazole, picrotoxin, strychnine. There are also drugs, described to lower seizure threshold such as aminophylline, antidepressants, sedating antihistamines, antimalarial drugs, some antipsychotics (eg, clozapine), buspirone, fluoroquinolones, theophylline (Ruffman et al 2006). In a study from 1977, seizures were recorded in less than 1% of 32 812 consecutive patients prospectively monitored for drug toxicity in selected medical wards (Porter et Jick 1977).

Antiepileptic medications are a heterogeneous pharmacologic class characterized by various chemical structures and postulated mechanisms of actions (Paterno et al, 2010). The main therapeutic applications of antiepileptics include epilepsy, bipolar disorder, depression, neuralgia, and migraine (Ettinger et al, 2007). Antiepileptic drugs (AEDs) are among the most commonly prescribed centrally active agents. In a survey, carried out in a Danish County, 1.1% of the studied people received AEDs. The use of these drugs increased with increasing age (Rochat et al 2001).

Proton pump inhibitors (PPIs) and H₂-receptor antagonists (H₂RAs) are widely prescribed acid-suppressive medications that in general have good safety profiles (Yang and Metz, 2010). AstraZeneca has received spontaneous reports of convulsion/seizure reported in patients taking esomeprazole and omeprazole. As commonly observed in postmarketing reports, information with regard to possible underlying cause, concomitant medication and potentially contributing factors were limited. In AstraZeneca placebo-controlled studies comprising esomeprazole or omeprazole no reports of convulsion/ seizure in patients given PPIs were found.

There are 3 articles based on Prescription Event Monitoring (PEM) addressing the association between proton pump inhibitors (PPI) and the occurrence of adverse events. The first report included patients (n=16,204) who had been treated with omeprazole by general practitioners in England between June 1989 and June 1990 (Wilton et al 1993). Among the events recorded during a six months period there were 17 records of convulsions. The authors stated that “in five cases the possibility of a link with omeprazole cannot be excluded”. In another PEM report assessing the safety profile of esomeprazole that included 11,595 patients, there is no mention of seizures/convulsions recorded as adverse events (Davies et al 2008), and in another PEM report with 11,541 patients treated with pantoprazole one case of epilepsy (new event) was reported (Wilton et al 2003).

Case reports of neurotoxicity including seizures in relation to histamine 2 receptor antagonists have been reported (Edmonds et al 1979). In a post-marketing surveillance report of the safety of cimetidine including 9928 patients taking cimetidine and 9351 controls there was no association reported between cimetidine and epilepsy. Major convulsions recorded for the first time as a primary diagnosis were reported in five users of cimetidine and three controls (Colin Jones et al 1985).

This observational study will further investigate the potential association between seizures and acid suppressing drugs in clinical practice and contribute to quantify the potential risk of seizures associated with the use of acid-suppressing drugs (PPI and H₂RA).

3. STUDY OBJECTIVES

- To estimate the incidence of seizure in the general population and stratified by epilepsy status
- To estimate the relative risk of seizure associated with use of PPI and H₂RA and stratified by epilepsy status.

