4. METHODS

4.1 Study design

A nested case-control analysis in a retrospective cohort study will be performed using The Health Improvement Network (THIN) database in the UK. Data is prospectively recorded by participating primary care physicians as part of their routine patient care (see 4.2).

A nested case-control analysis will be conducted comparing incident cases of seizure versus controls selected with incidence density sampling. A graphical presentation of the study design is provided in Figure 1.

The rationale of our study design is:

- 1) to enhance the internal validity of users of acid-suppressing drugs by ascertaining individuals newly prescribed acid-suppressing drugs.
- 2) to maximize the power to quantify the risk of seizure associated with current use of acid-suppressing drugs by including all the experience available of acid-suppressing users.

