4.3 Study population

THIN will be used to identify all individuals aged 20–84 years from 1 January 2005 to 31 December 2011, who have been enrolled with their PCP for at least 2 years and have a computerized prescription history of at least 1 year. Patients will have to be free of acid-suppressing drugs (PPI or H₂RAs) for at least one year, and never have a diagnosis of cancer, alcohol abuse or alcohol-related disease, or drug abuse. When an individual meet all these eligibility criteria that date will be marked as start date. Patients aged ≥ 70 years with a follow-up longer than 1 year will be excluded from the study population if they have fewer than two recorded consultations with a PCP during their entire follow-up (proxy for incomplete and invalid data recording). All remaining individuals will constitute the final study population.

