4.3.2 Exclusion criteria

All patients fulfilling one of the following criteria will be excluded:

- Patients with at least 1 prescription of PPI or H₂RA in the year prior to start date
- Cancer before start date
- Alcohol abuse or alcohol-related disease before start date
- Drug abuse before start date
- Patients aged ≥ 70 years with a follow-up after start date longer than 1 year and fewer than 2 recorded consultations with a PCP during their entire follow-up

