4.4 Follow-up

All members of the study cohort will be followed up from the day after start date until the first occurrence of the following endpoints:

- First recorded entry of seizure (Table 2)
- Age = 85 years
- Cancer
- Alcohol abuse or alcohol-related disease
- Drug abuse
- End of the study period

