4.5 Outcome definition and ascertainment

Free text comments will be requested before reviewing patient profiles. Information will include demographic data and all clinical information. The profiles of computer detected patients with seizure/convulsion (Table 2) identified with the initial computer search and including free-text comments, will be reviewed manually to ascertain the number of potential cases with an incident episode of seizure. All patient personal identifiers will be suppressed and information on drug use removed to allow for a blinded revision of patient profiles. The date of onset of study outcome will be used as index date. Doubtful cases will be reviewed by two MD researchers and agreement will be reached. Patients will not be retained as seizure cases if they were admitted to hospital in the month before the index date; in-patient drug exposure is not available and therefore recent exposure in these patients would be unknown. All patients meeting our operational definition of seizure (see below) will be considered potential cases.

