4.5.1 Operational definition of incident case of seizure

A patient with an incident diagnosis of seizure during follow-up will be accepted as a case if the patient was referred to a consultant, and/or admitted to hospital for the event.

For the sub-analyses among patients with a diagnosis of epilepsy we will, however, also accept a broader case definition, i.e. an incident diagnostic code for a seizure during follow-up regardless of referral to specialist, or admission to hospital. The broader definition of seizure will be employed because we suspect that the threshold for seeking hospitalisation may differ between patients with epilepsy and non-epilepsy patients experiencing a seizure. Also, patients with epilepsy may already have attended specialist care when recruited into the cohort and will therefore not necessarily be referred to renewed specialist evaluation due to a further seizure in the follow-up period.

We will attempt to classify seizures into three categories:

- i. Acute symptomatic seizures:

Seizures occurring in close temporal relationship to one or more of the following:

CVD, traumatic brain injury, CNS-infection, severe systemic illness with fever, presenting symptom of multiple sclerosis (or within 7 days of relapse of this disorder), autoimmune diseases with signs of activation, metabolic causes (including hypoglycemia and low serum sodium), and cerebral hypoxia.

Close temporal relationship to the seizure is defined as 1 week for the majority of events listed, with certain exceptions. Longer intervals will be accepted in certain cases (e.g. subdural hematoma with no known trauma, cases of CNS-infection with signs of

persistent infection). Conversely, a shorter time-limit will be requested for hypoglycemia (24 hours). We will generally follow the recommendations of Beghi et al (2010) for the classification of acute symptomatic seizures.

ii. Unprovoked seizures:

Seizures not fulfilling the criteria for acute symptomatic seizures will be considered unprovoked seizures, if sufficiently documented with regard to the aforementioned possible causes of seizures listed under (i).

iii. Unclassifiable seizures:

Seizures with insufficient documentation to rule out acute symptomatic seizures.

Alcohol-related seizures or seizure in cancer patients will lead to exclusion.

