4.9 Statistical analysis

Incidence rate of seizure overall as well as age and sex-specific will be computed in the study cohort.

A nested case-control analysis will be performed to assess the effect of acid-suppressing drugs and potential risk factors for seizure using unconditional logistic regression. In this analysis all patients ascertained with an incident episode of seizures will be used as

cases. The control group will comprise a random sample of study cohort members, frequency-matched by calendar year (described in section 4.6). Under our study design of incidence density sampling, the odds ratio (OR) is an unbiased estimator of the incidence rate ratio (RR) (Rothman 2002).

To determine the association between study outcome and current use of PPI and H₂RA, we will run unconditional logistic regression models and compute the OR and their 95% confidence intervals (95%CI). The estimates will be adjusted for the frequency-matched variable (calendar year), age, sex, time to event and other independent risk factors described in section 4.7.

Sub-analyses will be repeated in the strata of individuals with epilepsy and individuals free of epilepsy for descriptive purposes.

Statistical analyses will be performed using Stata package version 11.0 (StataCorp LP, College Station, TX, USA).

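### Objective 1 promises seizure incidence in the general population, but the protocol computes it only in a restricted cohort with a restricted case definition

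*Protocol*

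**What the plan says.** The first objective, in Section 3 and again in the synopsis, is "To estimate the incidence of seizure in the general population and stratified by epilepsy status". Section 4.9 then fixes the denominator: "Incidence rate of seizure overall as well as age and sex-specific will be computed in the study cohort".

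Sections 4.3 to 4.3.2 define that cohort. Members are aged 20–84, with at least 2 years of registration and 1 year of prescription history. They must "never have a diagnosis of cancer, alcohol abuse or alcohol-related disease, or drug abuse". Section 4.3.2 excludes "Patients with at least 1 prescription of PPI or H₂RA in the year prior to start date", and also people aged 70 or over with more than a year of follow-up and fewer than two consultations. Under Section 4.4, follow-up stops at a cancer, alcohol or drug-abuse diagnosis, as well as at a seizure, age 85 or the end of the study.

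The cases are restricted too. Section 4.5.1 says "Alcohol-related seizures or seizure in cancer patients will lead to exclusion" and requires referral or admission for the event; a broader definition is accepted only in the epilepsy sub-analyses. Section 4.5 adds "Patients will not be retained as seizure cases if they were admitted to hospital in the month before the index date", because drug exposure in hospital is not available.

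**The concern.** The population named in the objective is not the population in which the rate is calculated. The restrictions were chosen for the drug question, and some of them bear on seizure risk. Section 2 lists drug withdrawal among the commonest causes of acute symptomatic seizures and names cocaine and other CNS stimulants as seizure-associated. The wording of Section 4.5.1 shows that alcohol-related seizures and seizures in cancer patients are expected and will be removed.

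The label matters because it would carry into the conclusions. Section 6.3 plans a publication, and Table 3 has the sponsor submitting the final report to the MHRA. A reader who meets a general-population incidence there may take it as a background rate, or compare it with the figures in Section 2: 29–39 per 100,000 per year for acute symptomatic seizures and 46–57 per 100,000 person-years for unprovoked seizures.

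**Working it through.** **1. Objective against design.**

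| Element | Objective 1 | What the protocol fixes |
|---|---|---|
| Age | no limit stated | 20–84 (4.3, 4.4) |
| Acid-suppressant use | no limit stated | none in the year before start date (4.3.2) |
| Cancer, alcohol, drug abuse | no limit stated | excluded at entry (4.3), censored afterwards (4.4) |
| Events counted | seizure | referred or admitted, except in the epilepsy sub-analyses; alcohol-related seizures and those in cancer patients removed (4.5.1) |
| Recent admission | no limit stated | cases admitted in the previous month removed (4.5) |

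Section 4.9 contains no standardisation, re-weighting or unrestricted denominator that would carry the cohort rate to a wider population.

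**2. The admission rule.** Its stated reason is missing in-patient drug exposure. That matters for a relative risk by drug use and is irrelevant to an incidence. The rule can remove seizures that follow a recent stroke or head injury, both among the leading causes in Section 2. No section removes the matching person-time, so events leave the numerator while the denominator stays.

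**3. The plan's own figure.** The only numerical target is in Section 4.9.1 and concerns the relative risk. With 100,000 person-years per group and 50 per 100,000, there are 50 events per group. The upper limit is exp(1.96 × √(1/50 + 1/50)) = exp(1.96 × 0.2) = 1.48, as stated. There is no corresponding figure for incidence.

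**4. How far the cohort rate could differ.** Let f be the share of person-time excluded and R the seizure rate in excluded people divided by the rate in included people. Then

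rate in all ÷ rate in cohort = (1 − f) + f × R,

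and the cohort rate is low by 1 − 1/[(1 − f) + f × R]. The documents give neither f nor R, so every value below is an assumption.

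| f | R = 1 | R = 2 | R = 3 |
|---|---|---|---|
| 5% | 1.00 (0%) | 1.05 (4.8% low) | 1.10 (9.1% low) |
| 10% | 1.00 (0%) | 1.10 (9.1% low) | 1.20 (16.7% low) |
| 20% | 1.00 (0%) | 1.20 (16.7% low) | 1.40 (28.6% low) |

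If the cohort rate were 50 per 100,000 (borrowed from Section 4.9.1), these ratios give 50.0 to 70.0 per 100,000 once the excluded people are added. The table covers the population exclusions only, not the case rules.

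**5. Direction.** The case rules can only take events away, and the drug-abuse and alcohol exclusions plausibly remove people at higher risk. Against that, no section says that acid-suppressant users have more seizures; that is the study question. Section 4.3.2 does not exclude people with earlier epilepsy or seizure, and Table 2 includes a code for fits in known epileptics. Their events could raise the cohort rate relative to the Section 2 background figures. The net direction is therefore not settled by the documents.

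**The case against.** The strongest defence is that nothing is hidden. The synopsis sets the exclusions beside the objective, Section 4.9 names the study cohort as the denominator, and the wording of the objective can be read as meaning overall as opposed to within epilepsy strata. The exclusions are reasonable for the relative-risk objective, and the planned age- and sex-specific rates lessen the age problem. All of this is fair, and it keeps the point small. It does not cure a population label that the design cannot deliver. Nor is this a detail left to a statistical analysis plan, since the protocol fixes both the objective and the denominator.

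A reader might infer more than the documents support:

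- **A contradiction with Section 4.1**, which speaks of "including all the experience available of acid-suppressing users". The rationale just before it limits the design to people newly prescribed these drugs, so the phrase reads naturally as all new-user experience, offered for power on the relative risk.
- **A contradiction with Section 5.** The statement on representativeness there is about PPI users and makes no claim about seizure incidence. What is missing from Section 5 is a caveat on the incidence estimate.
- **That acid-suppressant users are absent from the cohort.** The exclusion covers one year before entry. Past users can enter after a drug-free year, and members who start a drug later stay in follow-up.
- **That the elderly are left out.** Ages 65–84 are included, apart from some people aged 70 or over with few consultations.

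**Conclusion.** The objective is wrong as written. The design gives the incidence of a restricted set of seizures in a restricted cohort aged 20–84. It does not give incidence in the general population, and the result is not directly comparable with the two background ranges in Section 2. This follows from the text alone and needs no assumption.

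A reader might go on to conclude that the rate will be too low by a known amount. The documents do not support that. A lower rate is plausible, but the 4.8–28.6% in the working rests on assumed values of f from 5% to 20% and of R from 2 to 3. With R = 1 the population exclusions cause no bias, and with R below 1 the sign would reverse. The relative-risk objective is not affected by this point.

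**What to change.** In the synopsis and Section 3, restate objective 1 as seizure incidence in the defined study cohort, and name the restrictions: age 20–84, no acid-suppressant prescription in the year before entry, no cancer, alcohol-related or drug-abuse diagnosis, and the case rules of Sections 4.5 and 4.5.1. In Section 5, list these as a limit on the incidence estimate and say that it is not directly comparable with the Section 2 rates.

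Alternatively, to keep the wider objective, add one code-based rate in all THIN patients aged 20–84 who meet the registration and prescription-history requirements, without the drug, cancer and abuse exclusions or the matching censoring. Label it as unvalidated and state its age range.

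The first option costs wording and a narrower claim. The second costs one extra database count and gives a rate without case review. Either way, keep the restricted cohort for objective 2.
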